# **Statistical Methodology:**

Data will be presented as mean  $\pm$  SD or frequency (percent), where appropriate. Group differences will be compared using Student's t-test, or chi-square tests of association, where appropriate. Data will be assessed for departures from normality with group comparisons adjusted accordingly. The primary hypothesis efficacy endpoint is the incidence rate of nausea following surgery. Rates of nausea and 95% confidence intervals will be presented and group comparison will be via chi-square tests. The primary efficacy analysis will only include surgery groups sleeve gastrectomy and Roux-En-Y. However, to expand our knowledge regarding the effect of aromatherapy, we will recruit patients undergoing revisional bariatric surgery but these patients will only be considered for secondary analyses. As this is an RCT, we anticipate potential cofounders (e.g., gender, type of surgery, etc.) and effect modifiers to be distributed equally. However, in the event of a failed distribution of clinical or demographic characteristics, mixed effects modeling will be substituted to test the primary hypothesis. All analyses will be conducted using SAS (Ver.9.4, Carey, NC) with statistical significance considered as  $p \le 0.05$ , two-tailed.

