#### 3.3 Randomization

Upon enrollment in the trial, each subject will be randomized to one of two treatment groups: Product A (aromatherapy inhaler product), Product B (Placebo product: inhaler with distilled water). Each product will look the same. SAS will be used to generate the randomization table using random numbers to determine which treatment subject #1 will receive; subject #2 will receive, etc., resulting in a total of 90 subjects for each treatment group. The randomization scheme will be located in a secured location in the pharmacy department and access will be granted to Pharmacy and designated research team members.

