#### 3.4 Endpoints/Outcomes Measurements

# 3.4.1 Primary outcome.

Primary end-point: Post-operative bariatric patients that use aromatherapy will have a greater decrease in mean nausea levels compared to control group.

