# 4 STATISTICAL CONSIDERATIONS/DATA ANALYSIS

# 4.1 Sample Size

To test the primary hypothesis that aromatherapy will lead to a decrease in post-operative nausea among patients undergoing laparoscopic/robotic sleeve gastrectomy, Roux-En-Y, and/or revisional bariatric surgery we will use a Pearson Chi-Square test for proportion difference. Assuming an expected incidence of nausea among controls of 80%, an alpha level of 5 percent, and a 1:1 treatment to control group ratio, we anticipate 90 subjects per group (n= 180 total) provides at least 80% power will to detect a statistically significant 20% reduction in the incidence of nausea among aromatherapy patients. The randomization scheme was calculated with SAS (ver.9.4., Cary, NC) using a two-group (treatment vs. placebo), simple randomization block (n=15) design. The total randomization scheme was increased to 180 (15 blocks of 12 patients) to allow for drop out and screen failures. Sample size will be increased to 180 subjects, this allows for a 20% (n=30) adm/screen fail/etc. error.

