# 4.2 Method of Data Analysis

Data will be presented as mean ± SD or frequency (percent), where appropriate. Group differences will be compared using Student's t-test, or chi-square tests of association, where appropriate. Data will be assessed for departures from normality with group comparisons adjusted accordingly. The primary hypothesis efficacy endpoint is incidence rate of nausea following surgery. Rates of nausea and 95% confidence intervals will be presented and group comparison will be via chi-square tests. The primary efficacy analysis will only include surgery groups sleeve gastrectomy and Roux-En-Y. However, to expand our knowledge regarding the effect of aromatherapy, we will recruit patients undergoing revisional bariatric surgery but these will only be considered for secondary analyses. As this is an RCT, we anticipate potential cofounders (e.g., gender, type of surgery, etc.) and effect modifiers to be distributed equally. However, in the event of a failed distribution of clinical or demographic characteristics, mixed effects modeling will be substituted to test the primary hypothesis. All analyses will be conducted using SAS (Ver.9.4, Carey, NC) with statistical significance considered as p≤0.05, two-tailed.

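### Section 4.2 lets an undefined baseline imbalance swap the primary chi-square test for an unspecified mixed effects model; one pre-specified adjusted analysis should replace the switch

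*Combined protocol and SAP*

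**What the plan says.** - **Default test.** Section 4.1 states that "we will use a Pearson Chi-Square test for proportion difference", with 80% nausea in controls, a 20% reduction, 90 patients per group and at least 80% power. Section 4.2 agrees: "The primary hypothesis efficacy endpoint is incidence rate of nausea following surgery", compared by chi-square at a two-sided 5% level. It adds that "The primary efficacy analysis will only include surgery groups sleeve gastrectomy and Roux-En-Y".
- **Switch.** Section 4.2 expects randomisation to balance the groups ("we anticipate potential cofounders (e.g., gender, type of surgery, etc", an open-ended list), and then provides that "in the event of a failed distribution of clinical or demographic characteristics, mixed effects modeling will be substituted to test the primary hypothesis". The Statistical Methodology part of the Abstract repeats this: "mixed effects modeling will be substituted to test the primary hypothesis".
- **Other statement of the endpoint.** Section 3.4.1 says that patients using aromatherapy "will have a greater decrease in mean nausea levels compared to control group".
- **Allocation.** Section 3.3: "Upon enrollment in the trial, each subject will be randomized to one of two treatment groups". Neither 3.3 nor 4.1 names a stratification factor, so baseline characteristics are balanced only by chance.
- **Data available.** Form A (Appendix D) records the 0-3 nausea level before product and 5 minutes after it. Appendix H records surgery type and about a dozen other characteristics that precede the product.

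**The concern.** The mixed model replaces the chi-square; it is not an addition to it. Whether it does so depends on an imbalance for which there is no test, threshold, list of characteristics, timing or decision-maker. The replacement has no stated outcome, link, fixed effects, random effect or effect measure. Two competent statisticians could both comply with section 4.2 and report different primary results, possibly on different endpoints.

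The decision may also be taken with allocation in view. Form A carries the product letter beside both scores, section 2.3 says that A is the active product, and section 3.3 gives designated team members access to the randomisation scheme. Fixing the model only before formal unblinding would therefore protect little.

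**Working it through.** **1. The plan's own figure.** Inputs from 4.1 and 4.2: 80% in controls, 60% on treatment (20% read as absolute), n = 90 per arm, two-sided 5%. With pooled variance,

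power = Φ{[|p1−p2|√n − 1.96√(2p̄q̄)] / √(p1q1+p2q2)}
= Φ{[0.20×9.487 − 1.96×√0.42] / √0.40}
= Φ{(1.897 − 1.270)/0.632} = Φ(0.99) = 0.839.

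The stated power of at least 80% is reproduced. With the 30 patients allowed for losses removed, (180 − 30)/2 = 75 per arm gives 0.767.

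**2. What the plan fixes on each branch.**

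| | No imbalance | Imbalance |
|---|---|---|
| Method | Chi-square | Mixed effects model |
| Outcome | Incidence of nausea (4.1, 4.2) | Not stated |
| Covariates | None | Not stated |
| Random effect | None | Not stated |

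A mixed model needs clustered or repeated data. A binary model with, say, block or surgeon as random effect would keep incidence. A model using both scores per patient would probably use the 0-3 score, since product follows a complaint of nausea (3.1) and nausea yes/no before product would be yes for essentially everyone. That could lead to mean change, the endpoint of 3.4.1. The text allows either.

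**3. How often the switch might fire.** The plan gives no threshold. Assume it fires if any of k independent characteristics has p<0.05. Then P = 1 − 0.95^k:
- k = 2: 1 − 0.9025 = 0.098
- k = 8: 0.337
- k = 12: 0.460

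With 12 tests equally correlated at 0.2 to 0.5, the figure is 0.43 to 0.32.

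**4. What a mechanical switch would do.** The rule in step 3 was simulated with a logistic substitute.
- *90 per arm, 8 covariates, 3 of them prognostic (log-odds 0.3 or 0.6 per SD).* With no effect, the chi-square rejects in 4.6 to 4.9% of trials and the switch in 4.3 to 4.8%. At 80% vs 60%, power is 84 to 85% for both. The two disagree on significance in about 1% of null trials and 2 to 4% of trials with an effect (60% or 64% on treatment).
- *60 per arm (illustrative), 12 non-prognostic triggering covariates.* For odds ratios 1/1.5/2/3 per baseline point, chi-square power is 0.680/0.700/0.682/0.683. The switch gives 0.668/0.692/0.671/0.676 if the substitute omits the pre-product score and 0.667/0.695/0.682/0.694 if it includes it, a change of −1.3 to +1.1 points.

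**5. What one fixed adjusted analysis would do.** Logistic regression on pre-product level and surgery type; assumed baseline levels 1/2/3 in 40/40/20%; surgery type without effect; 80% vs 60%; 4,000 trials per setting.

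| Per arm | Chi-square, odds ratio 1/1.5/2/3 | Adjusted | Change (points) |
|---|---|---|---|
| 60 | 0.680/0.700/0.682/0.683 | 0.677/0.704/0.700/0.730 | −0.3/+0.4/+1.8/+4.7 |
| 75 | 0.779/0.778/0.764/0.768 | 0.783/0.787/0.790/0.815 | +0.4/+0.9/+2.6/+4.7 |
| 90 | 0.841/0.843/0.840/0.846 | 0.842/0.856/0.861/0.879 | +0.1/+1.3/+2.1/+3.3 |

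The adjusted test rejects in 4.8 to 5.8% of null trials, so part of the smallest gains is test size. A standardised risk difference from the same model had null rejection of 4.8 to 5.7% and 95% CI coverage of 94.3 to 95.2%.

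**The case against.** The strongest defence is that this is one contingency sentence with small numerical consequences, that a sensible statistician would keep incidence as the outcome, and that the chi-square could simply stay. Part of this stands. Keeping the chi-square as sole primary test, with a pre-specified adjusted sensitivity analysis, would also remove the switch. It would forgo the gain in step 5, and that gain rests on prognostic strengths that the documents do not give.

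Three stronger readings are tempting and are not supported.

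- *The switch inflates type I error or lets the team take the better result.* The text replaces one test by the other; it does not permit a choice between results. Under the assumed rule, type I error stays near 5%. The opposite claim, that the plan as written is safe, is not established either. Without a trigger or terms the plan cannot be followed mechanically, and no mixed model, change of endpoint or open choice of covariates was simulated.
- *The mixed model must test mean change.* A clustered binary model would keep incidence, and an ordinal model or a different cut-point could also use both scores. The change of endpoint is possible, not certain.
- *The pre-product score exists only for patients given product, so the analysis should be limited to them.* The Study Methodology part of the Abstract and section 3.1 have nausea rated before product is provided, product is then offered, and Form B asks whether it was used. A rated patient may go without product. Randomisation is at enrolment, so selecting on receipt conditions on a post-randomisation act that staff who know the letter could influence.

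**Conclusion.** The concern holds: the primary analysis is not fixed. An undefined imbalance selects between a specified test and an unspecified model, and the conflict between 3.4.1 and 4.2 means that the endpoint may change with it. The weight lies in this open discretion, not in a demonstrated error-rate problem.

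The chance of firing (about 10% with 2 characteristics, 46% with 12) assumes p<0.05 and independence. The finding of little effect on type I error or power assumes that rule with a logistic substitute. The gain from always adjusting (about 0 to +5 points, with −0.3 at worst when the score is not prognostic) assumes an odds ratio of 1 to 3 per baseline point. Gains of 8 to 10 points appear only if the two scores have a latent correlation of about 0.7. The plan should be changed before outcome data are seen; the design need not be.

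**What to change.** Delete the imbalance trigger from section 4.2 and the Abstract. Before any outcome data are seen:

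1. Reconcile 3.4.1 with 4.2 on the primary endpoint.
2. Pre-specify one primary analysis adjusted for pre-product nausea level (Form A) and surgery type (Appendix H). For any nausea at 5 minutes, use logistic regression with a standardised risk difference and 95% CI. For the mean level, use ANCOVA of the 5-minute score and restate the sample-size basis in 4.1.
3. Keep the unadjusted test as a sensitivity analysis.
4. Analyse all randomised sleeve and Roux-En-Y patients who reported nausea and were rated on the unit, in their randomised arm, whether or not they then received or used product. Report by arm how many did not report nausea and how many did not receive product.
5. Recheck power at the number expected in that population. The 90 and 75 per arm still include revisional patients and patients who never report nausea.

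No new data are needed, since both covariates are already collected. The cost is a defined endpoint and population and revised analysis wording, plus a new sample-size calculation if the mean-level endpoint is kept. If the score turns out not to be prognostic, the loss is about 0.3 points of power.

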#### 4.3 Data Storage

Data will be stored in a secure area in a locked cabinet. All electronic data will be stored on a password protected, secure server. All computers will be password protected. REDCap, a HIPAA compliant, secure web-based application for building and managing online surveys and databases will be used to store the data.

# 4.3.1 Data Management

Information about study subjects will be kept confidential and managed according to the requirements of the Health Insurance Portability and Accountability Act of 1996 (HIPAA). Privacy and confidentiality of all enrolled participants will be maintained. Participants will be de-identified using an ID# that will only be accessible to the research team. The key to the PIN will be kept separate from the collection data and secured in a locked cabinet. All data will be stored on a password protected secure server. REDCap will be used. A Data Usage Agreement (DUA) will be executed by Inova to an external consultant in order to ensure the privacy and protection of data.

#### 4.3.2 Records Retention

Data will be stored for three years and then will be destroyed.

# 5 HUMAN SUBJECTS PROTECTION (RISKS, BENEFITS, AND ALTERNATIVES)

#### 5.1 Risks

Minimal risks, if any, are anticipated. Participants may experience dizziness, lightheadedness and/or headache.

#### 5.2 Benefits

There is potential for participants in this study to receive direct benefits from participating in the study by decreasing nausea levels.

#### 5.3 Alternatives

The alternative is to not be a participant in the study.

#### 5.4 Confidentiality

Confidentiality of the data will be ensured as follows:

- All study data will be coded with a PIN. The PIN will be used in lieu of any identifiable information to ensure confidentiality.
- Only the research team will have access to hardcopy study data. Hardcopy study data will be kept in a locked file cabinet or locked area.
- Only the research team will have access to electronic databases with the study data. The electronic database will be held on a password protected computer. REDCap will be used.
- Data will be made available only to the investigators and staff working on the study.
- Data will be reported in aggregate.

# **6 SUBJECT COMPENSATION**

## 6.1 Costs

There are no costs to participants.

# 6.2 Payment

There will be no payment for participation.

## 7 ADVERSE EVENT REPORTING

There are no known anticipated potential adverse events as a result of this study. However, any adverse events will be reported to the IRB. Protocol deviations will also be reported as required.

## 8 FUNDING

This proposed study is non-funded.

The company Soothing Scents will be donating the QueaseEASETM aromatic inhalers and placebo inhalers free of charge under the Ease the Quease product evaluation program. Disclaimer states: "enrollment in this program in no way obligates your facility to purchase any product or pay any fees to soothing scents (product costs, set-up cost, shipping & handling, etc.). You can stop the program at any time. Soothing Scents also reserves the right to cancel the program at any time" (refer to appendix J: Soothing Scents Disclaimer).

#### 9 CONFLICTS OF INTEREST

There are no conflicts of interest. Refer to disclaimer from Soothing Scents (refer to appendix J: Soothing Scents Disclaimer).

# 10 FACILITIES AND EQUIPMENT

The Surgical Unit at Inova Fair Oaks Hospital will be the study site. No extra equipment or investigational equipment is needed for this study.

# 11 OUTSIDE CONSULTANTS/COLLABORATORS

All members of the research team have completed CITI or WCG training and are Inova employees.

#### 12 CONTRACTURAL AGREEMENTS

There are no contractual agreements.

# 13 CLINICAL TRIALS

A description of this clinical trial will be available on https://www.clinicaltrials.gov/ as required by U.S. law.

# Appendix B

Please contact me with more information about the Aromatherapy Research Study!  Please Print-
First Name:
Last Name:
Date of Birth (month/date/year):
I prefer to be contacted by: Email Phone My Chart

# Appendix D

Appendix D

	Patient Identification Number (PIN):
Aromatherapy and nausea level stud	ly on Surgical Unit for post-operative Inova
Medical Grou	up Bariatric Surgery

# Data Collection Form A

intervention	
Nausea level before aromatherapy:	0 1 2 3 No Nausea Some Alot Severe
Date:/ Time:	— , s
Administer Aromatherapy product/ Intervent	
Aromatherapy product given:	Product A Product B
Date:/ Time:	— 4
Reassess nausea level after aromatherapy:	
Nausea level 5 minutes after aromatherapy:	0 1 2 3 No Nausea Some Alot Severe
Date:/ Time:	- .a
Did the patient request an antiemetic after the are	omatherany intervention?
YES NO	omaticapy mes content.
Date:// Time:	W4
xx	_ ,
	Add Patient Label

# Appendix E

Patient Identification Number	
(PIN):	

# Aromatherapy and nausea level study on Surgical Unit for post-operative Inova Medical Group Bariatric Surgery

# Data Collection Form B

Did you use the QueaseEASE product?  If yes-  How beneficial was the aromatherapy?  O 1 2 3 4 5 maximal or very beneficial  Would you consider using QueaseEase™ in the future for nausea?  Yes/No  Would you recommend QueaseEase™ to family / friend?  Yes/No  Did participate experience any side effects from the product?  Yes/No  If yes, what was the side effect (s): Dizziness  Light-headedness  Headache  Other  Please provide any additional comments or feedback below:	TO ASK ON DAY OF DISCHARGE Aromatherapy (QueaseEase™) Questions: following questions:	: Research M	lember to a	sk the patient th	ie
How beneficial was the aromatherapy?  0 1 2 3 4 5 maximal or very beneficial  Would you consider using QueaseEase™ in the future for nausea? Yes/No  Would you recommend QueaseEase™ to family / friend? Yes/No  Did participate experience any side effects from the product? Yes/No  If yes, what was the side effect (s): Dizziness Light-headedness Headache Other	Did you use the QueaseEASE product?	Yes	No		
maximal or very beneficial  Would you consider using QueaseEase™ in the future for nausea? Yes/No  Would you recommend QueaseEase™ to family / friend? Yes/No  Did participate experience any side effects from the product? Yes/No  If yes, what was the side effect (s): Dizziness Light-headedness Headache Other	If yes-				
Would you recommend QueaseEase™ to family / friend? Yes/No  Did participate experience any side effects from the product? Yes/No  If yes, what was the side effect (s): Dizziness Light-headedness Headache Other	How beneficial was the aromatherapy?	2078	2 3 4	maximal or	
Did participate experience any side effects from the product?  Yes/No  If yes, what was the side effect (s): Dizziness Light-headedness Headache Other	Would you consider using QueaseEase™ in	the future fo	or nausea?	Yes/No	
If yes, what was the side effect (s): Dizziness Light-headedness Headache Othe	Would you recommend QueaseEase™ to fa	mily/friend	!?	Yes/No	
	Did participate experience any side effects i	from the proc	luct?	Yes/No	
Please provide any additional comments or feedback below:	If yes, what was the side effect (s): Dizzines	ss Light-h	eadedness	Headache	Other
	Please provide any additional comments or	r feedback be	elow:		

# Appendix G

# Study Recruitment Script:

"I am collaborating with nurse researchers at Inova on a research study to explore the effects of an investigational aromatherapy on nausea in the post-operative bariatric patient population on the surgical unit. Aromatherapy is the therapeutic use of essential oils from plants.

If you agree to participate in the study you will be randomized (assigned by chance) to a product group (product A or product B) and will receive either the active intervention or placebo. There is a 50% or 1 in 2 chance of you receiving either product A or product B upon your initial complaint of nausea when on the surgical unit. You will receive a one-time dose for your nausea using either product A or product B based on trial randomization. This intervention will be in addition to your usual care and also not interfere with your care.

In order to participate in this study, you will need to provide informed consent.

I am happy to answer any questions you may have about the study and review the consent form with you."

# Appendix H

# Appendix H

# Demographic/Outcomes Sheet

Name:					 			
MRN #	0 40 40	8608	227 2	- 2 - 2				
Date of Admiss	sion:					Privat	e Room	Semi-Private
Gender:	Female		Male		Unidentified		Declined	
Age:								
Race: Ameri White		an	Asian		African Ameri	can	Other Pacifi	c Is lande r
Ethnicity:	Hispan	ic		Not H	ispanic			
ВМІ:								
Surgery Date:								
Type of surger	y:	Sleeve	gastre	tomy	Roux-En-Y	Revisi	onal bariatric s	surgery
ICD Codes:		27 074160	100				ev: 43860	
	Band r	emoval	to sleev	e: 437	75 + 73774	Band	emoval: 7377	2
	Band r	emoval	+ comp	onents:	73774			
Method:	Laparo	scopic		Robot	tic			
Hiatal herniar	epair:	Yes		No				
Length of surg	ery (tota	l minute	es):			-		
Type of anesth	nesia:	Gas	TAP	On Q	pump			
Botox injection	n:	Yes		No				
Amount of IVF	adminis	tered in	the OR					
Antiemetic red	eivedin	PACU:	YES	No				
If YES, name of	f antiem	etic rec	eived		/ dose	 		/time
Aromatherapy	interve	ntion pr	oduct:		productA	or	product B	
Initial antieme	tic admii	nistered	on the	surgical	unit:			
time	_/drugi	name_		/ do	se			

# Appendix H

Time spar	n (total minutes) between	QueaseEA	SE™ aromather	apy and first ant	ieme t ic on surgical unit:
Subseque	ent antiemetics administe	red on the s	surgical unit (fir	st 24 hours):	
time	/drug name	/dose			
Subseque	ent antiemetics administe	red on the	surgical unit (fir	st 24 hours):	
time	/drug name	/dose			
Subseque	ent antiemetics administe	red on the	surgical unit (fir	st 24 hours):	
time	/drug name	/dose	10000000		
Subseque	ent antiemetics administe	red on the	surgical unit (fir	st 24 hours):	
time	/drug name	/dose			
Subseque	ent antiemetics administe	red on the	surgical unit (fir	st 24 hours):	
time	/drug name	/dose	e Constanting		
Subseque	ent antiemetics administe	red on the	surgical unit (fir	st 24 hours):	
time	/drug name	/dose			
Number	of times patient received a	an antieme	tic after Queas	Ease™aromathe	erapy intervention
(first 24 h	ours)				
Date of d	ischarge:				
Did partio	ipate experience any side	effects?	YES	NO	
If yes, wh	at was the side effect(s)?		Dizziness	Headache	Lightheadedness
			Other		

